4.6. Other Analyses

No subgroup analysis is planned in this study

4.7. Interim Analyses

No formal interim analysis is planned; however, if recruitment is significantly slower than anticipated, then a single interim analysis may be conducted to assess variability, and which could result in a re-estimation of the sample size. Available PK concentration data from completed participants may be inspected to support development of depemokimab PK model. Model development details will be reported outside the CSR. No changes to the conduct of the study will be implemented because of these analyses

4.8. Changes to Protocol Defined Analyses

The study team will review PDs and SAEs to see if they have an impact on PK prior to data analysis.

If a PD or SAE is found in any subject during data review which has the potential to significantly impact the PK, then it will be decided whether we should exclude such subjects from the primary PK analysis. If the decision is to exclude, then the subject number of the subjects along with the reason of exclusion will be mentioned in the footnote of the output of the primary PK analysis

A sensitivity analysis for the primary endpoint may be conducted to evaluate the impact of subject exclusions.

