6.3. Blinding and Assignment to Study Intervention

6.3.1. Blinding:

This is an open-label study.

6.3.2. Assignment to Study Intervention:

Eligible participants will be randomly assigned to a treatment in accordance with the randomization schedule generated from the IRT system at GSK prior to the start of the study. Participants will be assigned to study intervention in accordance with the randomization schedule. Once a randomization number has been assigned to a participant, it cannot be reassigned to any other participant in the study.

Participants will be randomly assigned to receive 1 of 2 treatments with a ratio of 1:1 during the treatment period on Day 1 (Hour 0). Randomization will be stratified according to the participant's baseline body weight (<70 kg, 70 to <80 kg, and ≥80 kg). The site of injection will also be randomized in a 1:1:1 ratio to the upper arm, abdomen, or thigh. All treatments will be administered by authorized study site staff

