Primary	
The analysis for the primary PK endpoints will be performed for the PK Population.
 
Pharmacokinetic analysis will be performed to compare the relative bioavailability of a single subcutaneous dose of 100 mg depemokimab administered via an autoinjector compared to a single subcutaneous dose of 100 mg depemokimab administered via SSD.
 
Based on the individual concentration-time data the following primary plasma PK parameters will be estimated:
 
C_{max} and AUC(0-inf)
 
Analysis will be performed on the natural logarithms of AUC(0-inf) and C_{max} using a fixed-effects analysis of covariance model, with treatment and injection site as categorical covariates, and baseline weight as a continuous covariate fitted on the log scale. Effects will be estimated, and 90% CIs will be constructed for the following treatment comparisons:
 
Treatment B (Autoinjector) versus Treatment A (SSD)
 
Point estimates and 90% CIs for treatment differences on the log scale derived from the model will be exponentiated to obtain estimates for geometric mean ratios and CIs on the original scale.

Secondary	
The analysis for the secondary PK endpoints will be performed for the PK Population.

Endpoint	Statistical Analysis Methods
	Summary statistics for AUC(0-t), CL/F, Vz/F, λ_z , and t _{1/2} , (arithmetic mean, geometric mean, median, 95% CI [arithmetic and geometric], standard deviation [arithmetic and on ln-scale], minimum, maximum, and geometric CV). For T _{max} and T _{last} , median, minimum, and maximum only will be reported for each treatment group.

Further details of the PK analysis are provided in the SAP.

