
 To compare the pharmacokinetics of subcutaneous depemokimab following a single dose administered in the upper arm, thigh, or abdomen 	
 Depemokimab measured concentration at planned visits, by anatomical site of injection C_{max} and AUC(0-inf) of depemokimab in plasma, by anatomical site of injection

%AUCex = percentage of AUC(0-inf) due to extrapolation from Tlast to infinity; AUC(0-inf) = area under the concentration-time curve from time zero extrapolated to infinity; AUC(0-t) = area under the concentration-time curve from time zero to time of last observed quantifiable concentration; CL/F = apparent clearance following extravascular administration; C_{max} = maximum observed plasma concentration; λ_z = terminal elimination rate constant; T1/2 = terminal elimination half-life; Tlast = time of last measurable plasma concentrations; T_{max} = time to maximum observed plasma concentration; Vd/F = apparent volume of distribution following extravascular administration.

Primary Pharmacokinetic Estimand:

The primary question of interest is: to assess the relative bioavailability (assessed as ratio of the geometric mean of PK parameters maximum observed plasma concentration [C_{max}] and area under the concentration-time curve from time zero extrapolated to infinity [AUC(0-inf)]) of a single dose of depemokimab delivered with a SSD versus an autoinjector in healthy adult participants. The estimand is described by the following attributes:

Population	Healthy male and female participants 18 to 50 years of age inclusive
Treatment	Single subcutaneous dose of 100 mg depemokimab administered via a SSD versus via an autoinjector.
Intercurrent events (ICE)	
Use of prohibited medication: Use of prohibited medication is not expected to impact the PK of depemokimab; therefore, treatment policy strategy will be used and the individual PK concentrations after the occurrence of the intercurrent event will still be included into PK analysis.
 
 Handling of missing data: 
 For participants that withdraw prior to Week 18, or no PK concentrations are available until Week 18, it is anticipated that it will not be possible to derive the PK parameter AUC(0-inf). The participant will be excluded

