6.1.3. Protocol Deviations

Important protocol deviations will be summarized and listed.

Protocol deviations will be tracked by the study team throughout the conduct of the study. These protocol deviations will be reviewed to identify those considered as important as follows:

- Data will be reviewed prior to freezing the database to ensure all important deviations are captured and categorised in the protocol deviations dataset.
- This dataset will be the basis for the summaries of important protocol deviations.

No per-protocol analysis is planned for this study.

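### SAP 4.8 lets the study team drop participants with a protocol deviation or SAE from the primary PK analysis without preset criteria or masking, and makes the comparison with and without them optional

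*SAP*

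**What the plan says.** SAP 4.8 sets up a review: "The study team will review PDs and SAEs to see if they have an impact on PK prior to data analysis". Where a deviation or SAE might significantly affect PK, "then it will be decided whether we should exclude such subjects from the primary PK analysis". Excluded subject numbers and reasons go in a footnote to the primary output. On the effect of the exclusions it says: "A sensitivity analysis for the primary endpoint may be conducted to evaluate the impact of subject exclusions".

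Other parts of the plan describe a different primary analysis:

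- Protocol 9.3.2, repeated in SAP 4.2.2: "The analysis for the primary PK endpoints will be performed for the PK Population". The definition of that set (Protocol 9.2, SAP 3) requires dosing and at least one evaluable PK sample. It has no exclusion for deviations or SAEs.
- The estimand (Protocol 3, SAP 1.1) leaves a participant out of the AUC(0-inf) analysis when data do not reach Week 18, and out of the Cmax analysis when they do not reach Week 4, because the parameter cannot then be derived meaningfully. Its only intercurrent event is prohibited medication, for which "the individual PK concentrations after the occurrence of the intercurrent event will still be included into PK analysis".
- SAP 6.1.3: "No per-protocol analysis is planned for this study".

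On who could know what, Protocol 6.3.1 states "This is an open-label study", and SAP 4.7 adds "Available PK concentration data from completed participants may be inspected to support development of depemokimab PK model".

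**The concern.** The primary result is a between-device ratio of exposure, and Protocol 9.1 sets its 90% CI against 0.80 to 1.25. SAP 4.8 allows people who may know the device to choose, one case at a time, who contributes to that ratio. A deviation with the potential to change exposure is also one where the participant's value is likely to be extreme, so these choices bear on both the ratio and the width of its interval.

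The heading of 4.8 declares a change to the protocol-defined analysis, and the version history gives a reason for it. The estimand in SAP 1.1 was not changed to match. The reported primary result could therefore answer a different question from the one stated, and no second analysis is guaranteed to show by how much.

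**Working it through.** **Step 1. Who may be left out of the primary analysis, by section.**

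| Source | Grounds for leaving a participant out |
|---|---|
| Protocol 9.2 and 9.3.2; SAP 3 and 4.2.2 | Not dosed, or no evaluable PK sample |
| Estimand (Protocol 3, SAP 1.1) | Cmax or AUC(0-inf) not derivable |
| SAP 6.1.3 | None for deviations; no per-protocol analysis |
| SAP 4.8 | Any deviation or SAE judged able to affect PK, by case decision |

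The last row cannot be derived from the others. It also leaves device failure unaddressed. Protocol 10.7.3 classes malfunctions and use errors as device deficiencies, and Protocol 9.3.4 summarises them descriptively. No section says how an incomplete delivery enters the primary comparison, or that it cannot be recorded as a deviation.

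**Step 2. Reproduce the plan's interval.** Inputs from SAP 5: CV 30%, 63 per arm, ratio 1.00, two-sided 90%.

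- Log-scale SD = sqrt(ln(1 + 0.30²)) = 0.2936
- SE = 0.2936 × sqrt(2/63) = 0.2936 × 0.1782 = 0.0523
- Half-width = 1.657 × 0.0523 = 0.0867 (t with 124 df)
- exp(±0.0867) = 0.917 to 1.091, matching the stated 0.92 to 1.09

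**Step 3. Illustrate what one decision can do.** Suppose k of the 63 autoinjector participants receive a fraction f of the dose, exposure scales with dose, and the true ratio is 1 among intact deliveries. The documents give neither k nor f; both are assumptions. The comparison is unadjusted for weight and injection site.

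- Expected log ratio if kept = (k/63) × ln f
- Autoinjector variance if kept = 0.2936² + (k/63)(1 − k/63)(ln f)²
- Half-width = 1.657 × pooled SD × sqrt(2/63)

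For k = 3, f = 0.10:

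- Log ratio = (3/63) × (−2.303) = −0.1096, so the ratio is 0.896
- Autoinjector variance = 0.0862 + 0.0454 × 5.302 = 0.327
- Pooled SD = sqrt((0.0862 + 0.327)/2) = 0.454
- Half-width = 1.657 × 0.454 × 0.1782 = 0.134
- Interval = exp(−0.1096 ± 0.134) = 0.784 to 1.025

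If the three are excluded (60 against 63), the ratio returns to 1.00 with interval 0.916 to 1.091.

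**Step 4. Range of scenarios.** Simulation, 40,000 trials each, one parameter. Limits are averaged on the log scale. The last two columns give the probability that the 90% CI lies within 0.80 to 1.25.

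| Participants at fraction of dose | Ratio if kept (90% CI) | Kept | Excluded |
|---|---|---|---|
| 3 at 50% | 0.968 (0.883–1.061) | 0.97 | 0.99 |
| 5 at 50% | 0.946 (0.861–1.041) | 0.92 | 0.99 |
| 3 at 25% | 0.936 (0.841–1.041) | 0.83 | 0.99 |
| 5 at 25% | 0.896 (0.797–1.007) | 0.47 | 0.99 |
| 2 at 10% | 0.930 (0.824–1.050) | 0.71 | 0.99 |
| 3 at 10% | 0.896 (0.783–1.025) | 0.34 | 0.99 |

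Mild partial deliveries barely matter. A few near-total failures do. Failures in the syringe arm would act in the opposite direction.

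**The case against.** A reader might infer that SAP 4.8 is a route for removing autoinjector failures. The text does not say so. It speaks of deviations and SAEs, applies to both arms and names no device. Device deficiencies have their own reporting route (Protocol 8.4.7 and 10.7), both devices hold the same pre-filled syringe (Protocol 6.1 and 6.1.1), and site staff give every injection. One can also argue that someone who received a fraction of 100 mg did not receive the treatment condition in the estimand, and that device function is a separate exploratory objective. That question is open; what stands is that the plan does not settle it.

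A reader might also see a flat contradiction over prohibited medication. The overlap is narrow. The estimand keeps those data because no effect on PK is expected, while 4.8 is triggered only by a potentially significant effect on PK.

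Nor do the documents show that the reviewers will see concentrations. Review comes before data analysis, early inspection is for PK model development in completed participants, and the noncompartmental and statistical work sits with two outside groups. The exclusions would not be hidden either: they are footnoted with reasons, important deviations are listed (SAP 6.1.3), and PK parameters are listed and individual values plotted (SAP 4.3.1.1 and 4.4).

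Finally, no formal hypothesis is tested, and Protocol 9.1 calls the 0.80 to 1.25 comparison an additional assessment. Talk of reversing a formal bioequivalence conclusion would go too far.

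These points limit the concern but do not remove it. Review before analysis is not the same as review before concentrations exist, and a footnote shows who left but not how far the ratio moved.

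**Conclusion.** The point holds as a gap in prespecification. SAP 4.8 permits unmasked exclusions from the primary analysis on unstated criteria, departs from the analysis set and estimand stated elsewhere, and leaves the analysis that would show the effect optional. This conflict exists whether or not any injection fails.

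Its numerical size is conditional. Under the assumptions in the working, three near-total autoinjector failures move the ratio from about 1.00 to 0.90 and the lower limit to 0.78. Three half-doses move the ratio to 0.97 with the interval well inside 0.80 to 1.25. The documents give no failure rate, so they do not support a claim that the result is likely to change, nor that bias is intended. It should be fixed because it touches the primary result and is cheap to close.

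**What to change.** Revise SAP 4.8 and the estimand in SAP 1.1 as follows:

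1. Keep the ANCOVA on all PK-set participants with a derivable parameter as the primary analysis, as in Protocol 9.3.2 and SAP 4.2.2.
2. Apply any PD or SAE exclusion only in a sensitivity analysis. Fix the reasons before concentrations are released to the reviewers, and apply them without reference to device.
3. Change the sensitivity analysis from *may be* to *will be* conducted, and report both results side by side.
4. State in the estimand how incomplete delivery or use error is handled. The documents leave the choice open, so the sponsor may decide either way, but in advance and for both arms.

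The cost is SAP wording and one extra model run. The primary interval may be slightly wider if partial deliveries occur and are kept.

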5. SAMPLE SIZE DETERMINATION

A total of approximately 126 (63 per treatment group) participants will be required to complete at least Week 18 of the study.

The primary aim of this study is to estimate the relative bioavailability of the autoinjector compared with the PFS. Therefore, the sample size calculation for this study is based on the number of participants needed to achieve an acceptable level of precision in the estimate of relative bioavailability.

The variability of depemokimab PK parameters (AUC and C_{max}) was informed by the depemokimab FTIH Study 205722 and the mepolizumab Phase 1 Study 204958 and is in line with results reported for monoclonal antibodies against soluble targets delivered subcutaneously.

Between subject variability (CV_b) of 30% was assumed for both AUC(0-inf) and C_{max} . Based on this CV_b , with a sample size of 63 participants per treatment group, the 90% CI for an estimated ratio of autoinjector versus PFS of 1.00 will be (0.92, 1.09).

In addition, assuming a within-subject correlation of 0.8 between AUC and C_{max} , and a true ratio of 1, a sample size of 63 participants will also provide 90% power to observe geometric CI of geometric mean ratio within the bioequivalence range of (0.8, 1.25) for both parameters.

Approximately 140 healthy participants will be enrolled (accounting for drop-out rate of 10% until Week 18) resulting in at least 126 evaluable participants (approximately 63 for each treatment group, 21 per injection anatomical site within each treatment group).

5.1. Sample Size Sensitivity

The table below provides the expected 90% CI estimates for a range of CV_b , assuming 5% difference in either direction in the ratio between autoinjector and PFS and $n = 63$ per treatment group.

CV_b	SDlogs	Estimated Ratio (Autoinjector/prefilled safety syringe)	Expected Two-sided 90% CI
0.30	0.293	0.95	(0.87,1.04)
		1.00	(0.92,1.09)
		1.05	(0.96,1.15)
0.35	0.339	0.95	(0.86,1.05)
		1.00	(0.90,1.11)
		1.05	(0.95,1.16)

6. SUPPORTING DOCUMENTATION

6.1. Appendix 1 Study Population Analyses

Unless otherwise specified, the study population analyses will be based on the Safety Analysis Set. A summary of the number of participants in each of the participant level analysis set will be provided based on Screened Analysis Set.

Study population analyses including analyses of participant disposition, demographic and baseline characteristics, protocol deviations, and prior and concomitant medications. Details of the planned displays are presented in OPS document.

6.1.1. Participant Disposition

A summary of the number and percentage of participants who completed the study as well as those who prematurely withdrew from the study will be provided. Reasons for study withdrawal and outcome of adverse events which led to study withdrawal will be summarized. Additionally, screening status and reasons for screen failure will be summarised.

Listings of reasons for screen failure and reasons for study withdrawal will be generated.

6.1.2. Demographic and Baseline Characteristics

The demographic characteristics including age, gender, ethnicity, height, weight, body mass index (BMI) at screening and race will be summarized with descriptive statistics. In addition, the following age categories will be summarized: 18-64, 65-84 and ≥ 85 based on the Safety Analysis Set. Body Mass Index (BMI) is calculated as weight (kg)/ [height (m)]², will be presented as for summary statistics with 1 decimal place.

Past medical conditions and current medical conditions as of screening will be summarized as "Summary of Past and Current Medical Conditions".

6.1.3. Protocol Deviations

Important protocol deviations will be summarized and listed.

Protocol deviations will be tracked by the study team throughout the conduct of the study. These protocol deviations will be reviewed to identify those considered as important as follows:

- Data will be reviewed prior to freezing the database to ensure all important deviations are captured and categorised in the protocol deviations dataset.
- This dataset will be the basis for the summaries of important protocol deviations.

No per-protocol analysis is planned for this study.

6.1.4. Prior and Concomitant Medications

Prior and concomitant medication tables will report by Anatomical Therapeutic Chemical (ATC) level 1 and ingredient. Multi-ingredient medications will be presented according to their combination ATC classification rather than the classification of the ingredients.

Summaries will be provided for the concomitant medications taken during treatment.

6.1.5. Study Intervention Compliance

Not applicable

6.2. Appendix 2 Data Derivations Rule**6.2.1. Criteria for Potential Clinical Importance**

Reference ranges for all laboratory parameters collected throughout the study are provided by the laboratory. A laboratory value that is outside the reference range is considered either high abnormal (value above the upper limit of the reference range) or low abnormal (value below the lower limit of the reference range). Note: a high abnormal or low abnormal laboratory value is not necessarily of clinical concern.

In addition, the following criteria will be used to flag potential clinical importance:

6.2.1.1. Laboratory Values

Haematology				
Parameter	Units	Category	Clinical Concern Range	
			Low Flag (< x)	High Flag (> x)
Haematocrit	Ratio of 1	Male	0.33	0.54
		Female	0.33	0.54
		Δ from BL	↓0.075	
Haemoglobin	g/L	Male	110	180
		Female	110	180
		Δ from BL	↓25	
Lymphocytes	x10 ⁹ / L		0.8	
Neutrophil Count	x10 ⁹ / L		1.5	
Platelet Count	x10 ⁹ / L		130	550
While Blood Cell Count (WBC)	x10 ⁹ / L		3	15
%Reticulocyte	%		0.5	2.5
Reticulocyte	Fraction Of 1		0.005	0.025

Clinical Chemistry				
Parameter	Units	Category	Clinical Concern Range	
			Low Flag (< x)	High Flag (> x)
Albumin	g/L		30	
Calcium	mmol/L		2	2.75
Creatinine	umol/L	Δ from BL		↑ 44.2
Glucose	mmol/L		3	9
Potassium	mmol/L		3	5.5
Sodium	mmol/L		130	150

Liver Function			
Parameter	Units	Category	Clinical Concern Range
ALT/SGPT	U/L	High	≥ 3x ULN
AST/SGOT	U/L	High	≥ 2x ULN
AlkPhos	U/L	High	≥ 2x ULN
T Bilirubin	μmol/L	High	≥ 1.5xULN
T. Bilirubin + ALT	μmol/L	High	1.5xULN T. Bilirubin +
	U/L		≥ 2x ULN ALT

6.2.1.2. ECG

Parameter	Units	Clinical Concern Range	
		Lower	Upper
Absolute			
Absolute QTcF Interval	msec		> 450
Absolute PR Interval	msec	< 110	> 220
Absolute QRS Interval	msec	< 75	> 110
Absolute QT	msec		> 600
Change from Baseline			
Increase from Baseline QTcF	msec		> 60

6.2.1.3. Vital Signs

Parameter	Units	Clinical Concern Range	
		Lower	Upper
Systolic Blood Pressure	mmHg	< 85	> 160
Diastolic Blood Pressure	mmHg	< 45	> 100
Heart Rate	bpm	< 40	> 110

6.2.2. Study Period

Assessments and events will be classified according to the time of occurrence relative to dosing.

6.2.2.1. Treatment States for Safety Data

Treatment State	Definition
Pre-Treatment	Assessment/Event Date < Study Treatment Start Date
On-Treatment	Study Treatment Start Date ≤ Assessment/Event Date ≤ Date of Last Dose of Study Treatment + 182 days
Post-Treatment	Assessment/Event Date > Date of Last Dose of Study Treatment + 182 days

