 - n. Participants will be allowed to leave the clinic after all study procedures have been completed on Day 3.
 - o. Windows for clinic visits are as follows: Day 5 (96 hours; ± 4 hours); Day 8 (± 1 day), Day 15 (± 1 day); Day 29 (± 2 day); Day 57 (± 2 day); Day 85 (± 3 days); Day 127 (± 3 days); Day 169 (± 3 days), and Day 183 (± 5 days). There is no visit window applicable for Day 1 to Day 3 as they are in clinic assessments.
 - p. The last follow-up visit will consist of a telephone call to collect AEs/SAEs and concomitant medications. For WOCBP, this visit will be conducted in clinic so that a pregnancy test result can also be collected.
 - q. Follow-up call should be attempted if at all possible at Day 211 (W30) when patient early discontinues prior to reaching this time point to ensure patient's safety and well-being.
- The timing of planned study assessments may change during the course of the study based on emerging data/in-stream data review (e.g., to obtain data closer to the time of peak plasma concentrations) to ensure appropriate monitoring.
 - Any changes in the timing of time points for any planned study assessments as the result of emerging pharmacokinetic/pharmacodynamic data from this study must be documented and approved by the relevant study team member and then archived in the sponsor and site study files but will not constitute a protocol amendment.
 - The IRB/ IEC will be informed of any safety issues that constitute a substantial amendment and require alteration of the safety monitoring scheme or amendment of the ICF. The changes will be approved by the IRB/IEC before implementation.

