4.5.3. Laboratory Data

The haematology, clinical chemistry, urinalysis, and additional parameters to be tested are listed in Appendix 2 of the Protocol.

Summaries of laboratory data including chemistry and haematology parameters, and liver chemistry test data will be based on GSK Core Data Standards and unless otherwise specified will include on-treatment and post-treatment data.

Change from baseline for Chemistry and Haematology will be summarized.

Change from baseline for laboratory values will be summarized by visit.

Summary of worst-case laboratory results relative to PCI Criteria post-baseline relative to baseline will be done using categories of “To Low”, “To Within Range or No Change” or “To High”.

Summary of worst-case laboratory results relative to normal ranges post-baseline relative to baseline will be done using categories of “To Low”, “To Normal or No Change” or “To High”.

The derivation rule follows:

- Laboratory values will be classified as “Low”, “Normal”, or “High” based on the provided normal ranges.

Laboratory values will be classified as “Low”, “Within Range”, or “High” based on the provided PCI ranges.

- Change from baseline values will be classified relative to normal range as “To Low”, “To Normal or No Change”, or “To High”. Participants who do not change categories or move from out-of-range to normal will be classified as “To Normal or No Change”.

Change from baseline values will be classified relative to PCI ranges as “To Low”, “To Within Range or No Change”, or “To High”. Participants who do not change categories or move from out-of-range to normal will be classified as “To Within Range or No Change”.

- A “worst case post-baseline” change classification relative to normal ranges will be derived for each treatment in which participants will be counted in the “To Low” or “To High” categories if they reported a change from a “Normal” baseline to a value below or above the normal range, respectively, at any on-treatment scheduled, unscheduled, or early withdrawal visits. Participants who did not report a change to a value outside the normal range at any visit will be counted in the “To Normal or No Change” category.

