6.2.3. Study Day and Reference Dates

The safety reference date is the study intervention start date and will be used to calculate study day for safety measures.

The study day is calculated as below:

- Assessment Date = Missing → Study Day = Missing
- Assessment Date < Reference Date → Study Day = Assessment Date – Ref Date
- Assessment Date ≥ Reference Date → Study Day = Assessment Date – Ref Date + 1

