6.2.5. Multiple measurements at One Analysis Time Point

Mean of the measurements (e.g., ECG) will be calculated and used in any derivation of summary statistics but if listed, all data will be presented.

If there are two values within a time window the value closest to the target day for that window will be used. If values are the same distance from the target, then the mean will be taken.

Participants having both High and Low values for Normal Ranges at any post-baseline visit (including post-baseline unscheduled assessments) for safety parameters will be counted in both the High and Low categories of “Any visit post-baseline” row of related summary tables. This will also be applicable to relevant Potential Clinical Importance summary tables.

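### The worst-case shift tables stop at Study Day 183, so a scheduled exit assessment made in window on Days 184 to 188 is not counted, and SAP 4.5.3, 6.2.4 and 6.2.5 disagree on which visits count

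*SAP*

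**What the plan says.** SAP 6.2.2.1 places the end of the on-treatment period at "Date of Last Dose of Study Treatment + 182 days". It defines on-treatment safety data as "Study Treatment Start Date ≤ Assessment/Event Date ≤ Date of Last Dose of Study Treatment + 182 days" and post-treatment data as "Assessment/Event Date > Date of Last Dose of Study Treatment + 182 days". No allowance is made for a visit window. SAP 6.2.3 counts days from dosing by "Study Day = Assessment Date – Ref Date + 1".

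In the protocol's Schedule of Activities (Section 1.3), the footnote that opens "Windows for clinic visits are as follows" closes its list with "and Day 183 (± 5 days". That is the Week 26 exit visit.

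SAP 4.5.3 begins with a general rule that laboratory summaries include both on-treatment and post-treatment data unless something else is specified. It then specifies the worst-case shift classification. A participant goes into *To Low* or *To High* if a change from an in-range baseline is seen "at any on-treatment scheduled, unscheduled, or early withdrawal visits". The PCI version uses the same restriction, and so does the rule for participants with both high and low values. The no-change category is defined by the absence of an out-of-range change at any visit. Sections 4.5.5 (vital signs) and 4.5.6 (ECG) say that their PCI derivation is similar to the laboratory one.

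Two other sections are wider. SAP 6.2.4 puts unscheduled and early-withdrawal data into maximum and worst-case post-baseline summaries, whether or not they have been slotted to a visit. SAP 6.2.5 is written for "Participants having both High and Low values for Normal Ranges at any post-baseline visit (including post-baseline unscheduled assessments) for safety parameters" and extends this to the PCI tables.

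**The concern.** A worst-case table is meant to show the most extreme value after dosing. Here the period it draws on ends on the target day of the last scheduled safety visit, not at the end of that visit's window. Whether an exit value is eligible would then depend on the calendar day of attendance, with no clinical or protocol reason for the difference.

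The ECG is the most exposed assessment. In the Schedule of Activities the exit ECG is the only scheduled one after Day 85. For a participant who attends late but in window, the ECG worst-case PCI table could therefore rest on scheduled tracings up to Week 12 only. The safety endpoints are framed over a 26-week period, and this visit is its end.

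The conflicting wording is a second problem: two programmers could build different tables from the same SAP.

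**Working it through.** **Inputs**
- On-treatment limit: dose date + 182 days, inclusive (SAP 6.2.2.1).
- Study Day = date − dose date + 1 (SAP 6.2.3).
- One dose, on Day 1, so first and last dose dates coincide (Protocol 4.1).
- Exit visit window: Day 183 ± 5 (Protocol 1.3).
- Preceding clinic visit: Day 169 ± 3 (Protocol 1.3).

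**Step 1: the plan's own cut-off.** 182 + 1 = Study Day 183. Week 26 is 26 × 7 + 1 = Day 183. The SAP limit and the nominal exit day are the same day.

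**Step 2: the window against the cut-off.** 183 − 5 = 178 and 183 + 5 = 188, so the window is Days 178 to 188, or 188 − 178 + 1 = 11 days. Days 184, 185, 186, 187 and 188 lie beyond the cut-off. That is 5 of 11 permitted days, 5/11 = 45% of the window. Day 188 is dose + 187.

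**Step 3: other scheduled visits.** The latest in-window day for the preceding visit is 169 + 3 = 172, which is before 183. The Day 211 follow-up collects adverse events and concomitant medication, with a pregnancy test for women of childbearing potential; no ECG or vital signs are marked there. The exit visit is the only scheduled visit with these assessments that can cross the limit.

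**Step 4: the rules applied to one case.** Take a participant in range at baseline whose only out-of-range value falls on Day 186.

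| Rule | Scheduled exit visit, Day 186 | Unscheduled visit, Day 186 |
|---|---|---|
| 4.5.3, low/high categories | not counted (post-treatment) | not counted (post-treatment) |
| 4.5.3, no-change category | does not fit (a change was seen at a visit) | does not fit |
| 6.2.4 | not addressed | counted |
| 6.2.5 | any post-baseline visit | any post-baseline visit |

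Read literally, 4.5.3 leaves this participant in no category. If *at any visit* is taken as short for any on-treatment visit, the participant is reported as unchanged. Under 6.2.4 an unscheduled value on Day 186 counts, while a planned, in-window value from the same day has no such provision.

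**Step 5: what is not affected.** The SAP states no on-treatment limit for:
- change-from-baseline summaries by visit;
- maximum QTcF, maximum QT and maximum QTcF-change categories;
- the ALT and bilirubin maximum plots;
- hepatobiliary abnormalities and worst-case urinalysis.

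Adverse event, SAE and AESI tables cover any time after dosing. Among the ECG parameters with PCI limits in 6.2.1.2, QTcF and QT therefore have another maximum display. PR and QRS do not, although they remain in the by-visit summaries.

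**The case against.** The best defence is that 4.5.3 starts from the inclusive position, on-treatment plus post-treatment data, and that 6.2.4, 6.2.5 and the no-change wording all point the same way. On that view the restriction is a loose word and the data would be included. This does not fully answer the point. The inclusive sentence gives way where something else is specified, and the worst-case rule does specify something else. What stands is that the wording is unreconciled, so exclusion is what the specific rule says, not a certainty about the final tables.

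Section 6.2.5 may also describe a different table row (any visit post-baseline) from the one in 4.5.3 (worst-case post-baseline). If so, the two do not strictly contradict each other, and late values would still appear in the 6.2.5 row. The SAP does not say whether the rows are the same.

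A third argument is that 182 days is exactly 26 weeks and matches the endpoint period, so it is not an obvious slip. That is fair, and it is a reason to leave the phase definition alone.

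A reader might infer that late exit data vanish from the safety reporting, or that 45% of participants lose their exit assessments. The documents support neither. The values stay in the by-visit summaries and the displays listed under step 5, and 45% is a share of permitted days, not of people.

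**Conclusion.** The point holds for one type of display: the worst-case shift classification against normal ranges and PCI limits. As specified, it does not count in-window scheduled exit assessments on 5 of the 11 permitted days, and it conflicts with 6.2.4, with 6.2.5 if the rows are the same, and with its own no-change definition.

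The number of participants affected is unknown because no visit dates are given. A late visit changes a table only if the participant was in range at baseline, is out of range at exit, and was not already out of range in the same direction earlier. The count of changed classifications cannot exceed the number of late attenders and will usually be below it.

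Two assumptions remain. For vital signs and ECG, the restriction arrives only through the word *similar*. For laboratory tests, the copy of the Schedule of Activities available for this review lacks the laboratory rows, so exit-visit samples are presumed from the 26-week laboratory endpoint, not confirmed.

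Severity is minor: descriptive safety tabulation, with no bearing on the primary PK comparison.

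**What to change.** In the worst-case rules of SAP 4.5.3, for both normal range and PCI and including the rule for participants with both high and low values, replace the restriction to on-treatment visits with any post-baseline visit, whether scheduled, unscheduled or early withdrawal. State in 4.5.5 and 4.5.6 that the same rule applies, in place of *similar*. This agrees with 6.2.4 and 6.2.5 and gives every participant a category.

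Leave the phase definitions in 6.2.2.2 and 6.2.2.3 unchanged. Moving the limit to dose + 187 there is unnecessary: it would alter which medications count as taken during treatment and the phase labels of adverse events, and the adverse event tables already cover all post-dose time.

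The cost is one phrase, two cross-references and the matching filter in the table programs, best settled before database freeze.
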